13. VIROLOGY

The virology analyses will mainly use genotype and phenotype data based on plasma sample for CVF population, unless otherwise specified. Additional analyses for HIV-1 resistance may be carried out on peripheral blood mononuclear (PBMC) samples collected at Day 1, Week 48, Week 96, or Withdrawal if prior to Week 96.

If pre-treatment genotypic/phenotypic results are available from both the central laboratory and Monogram Biosciences, then Baseline genotype/phenotype will be determined based only upon the data provided by Monogram assays.

Table 7 provides an overview of the planned analyses, with further details of data displays being presented in Appendix 14: List of Data Displays.

Table 7 Overview of Planned Virology Analyses

Endpoint	Absolute			
	Summary		Individual	
	T	F	F	L
Genotypic resistance at time of CVF^[1]				
Prevalence of Resistance Mutations	Y ^[2]			Y
Prevalence of Genotypic Susceptibility	Y			
Phenotypic resistance at time of CVF^[1]				
Prevalence of Phenotype	Y ^[3]			Y
Fold Change to CAB and RPV	Y			Y ^[4]
IN, PR/RT Replication Capacity				Y
Other				
Viral load, Genotypic and Phenotypic data for Participants with genotype and/or phenotype data for CVF and non-CVF participants				Y ^[4]
Net Assessment	Y			

NOTES:

- T = Table, F = Figure, L = Listing, Y = Yes display generated.
 - Summary = Represents TFL related to any summaries (i.e. descriptive statistics) of the observed raw data.
 - Individual = Represents FL related to any displays of individual participant observed raw data.
1. For the CVF as indicated by two consecutive plasma HIV-1 RNA levels ≥ 200 c/mL after prior suppression to < 200 c/mL, the first visit of these two consecutive visits is defined as 'the suspected visit', and the 2nd one is the confirmed visit. Sample used for resistance testing is taken at the suspected visit, and only tested once a participant confirms virological failure at a subsequent visit. If the test fails with the sample at the suspected visit, we will just report it as 'no data'. The sample from the confirmed visit may be used for exploratory analyses.
 2. No. and percentage of participants with IN resistance mutations or major mutations in the classes of NNRTI, NRTI, PI, respectively, as defined in Section 15.6.7.
 3. Separate outputs by phenotypic susceptibility and by number of drugs to which participants are phenotypic resistant or partial sensitive or sensitive.
 4. Fold change to CAB and RPV will be included in the listing for viral load, genotypic and phenotypic data for participants with genotype and/or phenotype data for CVF and non-CVF participants.

15. APPENDICES

15.1. Appendix 1: Protocol Deviation Management and Definitions for Per Protocol Population

15.1.1. Exclusions from Per Protocol Population

Important protocol deviations leading to exclusion from the Per Protocol population are those deviations which may

- directly impact the efficacy endpoint of HIV-1 RNA; or
- lead to permanent discontinuation of IP/withdrawal and hence indirectly impact the efficacy endpoint by causing data to be missing.

The following criteria define the important protocol deviations which, if they occur prior to an analysis timepoint of interest (e.g. Week 48/96), will lead to exclusion of a participant from the Per-Protocol population for that analysis. Potential protocol deviations leading to exclusion from PP population will be reviewed by the study team to confirm that they meet these criteria. A final review will occur before the clinical database has been frozen for analysis.

A participant meeting any of the following criteria will be excluded from the Per Protocol population based on case-by-case clinical determination:

Number	Exclusion Description
01	Participant deviates from any inclusion or exclusion criteria that may significantly affect exposure, response to therapy or participant safety or that are fundamentally inconsistent with the intended study population, as recorded in the Protocol Deviation form in the eCRF based on study team review (where indicated in the PDMP as case-by-case determination).
02	Participant has maintenance phase non-compliance (including IM dosing errors) with investigational product up to an analysis timepoint of interest, meeting one of the following 3 conditions. For Week 48 analysis, the analysis timepoint of interest is the date of last on-treatment viral load up to Study Day 378 during maintenance phase, where Study Day 378 is the upper bound of snapshot window for Week 48 visit. For Week 96 analysis, the analysis timepoint of interest is the date of last on-treatment viral load up to Study Day 714 during the maintenance phase, where Study Day 714 is the upper bound of snapshot window for Week 96 visit. 
 1. Week 48 analysis only: 
 • Two or more injection intervals affected by over dosage deviations, for example 
 ○ Extra injection or excessive volume administered. ○ For Q8W participants requiring oral lead-in: length of time between Week 4B injection and Week 8 injection less than 3 weeks, or between injections post Week 8 less than 7 weeks, excluding split doses. ○ For Q8W participants not requiring oral lead-in: length of time between injections less than 7 weeks, excluding split doses. ○ For Q4W participants: length of time between injections less than 3 weeks, excluding split doses. 2. Week 96 analysis only: 
 • For participants who permanently discontinued study treatment on/before the

Number	Exclusion Description
	
analysis timepoint of interest for Week 48 analysis (i.e. the date of last on-treatment viral load up to Study Day 378): two or more injection intervals affected by over dosage deviations.
 
 • For participants who received injections beyond the analysis timepoint of interest for Week 48 analysis (i.e. the date of last on-treatment viral load up to Study Day 378): three or more injection intervals affected by over dosage deviations. 
3. $\geq 10\%$ of total time on-treatment with under dosing deviations. The percentage of total time on-treatment with under dosing deviations will be calculated by (the total number of non-compliant dosing days / the total number of intended exposure days) * 100%.
 
Number of Intended Exposure Days = Date of Last Viral Load – Start Date of Study Treatment + 1, where the last viral load refers to the last on-treatment viral load up to Study Day 378 during maintenance phase for Week 48 analysis, and the last on-treatment viral load up to Study Day 714 during maintenance phase for Week 96 analysis.
 
The total number of non-compliant dosing days up to the analysis timepoint visit (or date of IP discontinuation/ withdrawal, whichever is earlier), is derived as follows (summing across all instances):
 
 • For Q4W arm participants requiring oral lead-in: 
 ○ Length of time (in days) until next injection from date of dosage deviation (e.g. 2 mL administered instead of 3mL for Week 4B injection, 1ml administered instead of 2 mL for post Week 4B injections). ○ Length of time (in days) in excess beyond 35 days between injections post Week 12 and in excess beyond 28 days for Week 8 and Week 12 (e.g. missed or late injection visit). ○ Length of time (in days) in excess beyond 35 days from last injection until start of oral bridging post Week 12 and in excess beyond 28 days for Week 8 and Week 12. • For Q4W arm participants not requiring oral lead-in: 
 ○ Length of time (in days) until next injection from date of dosage deviation (e.g. 1 mL administered instead of 2 mL). ○ Length of time (in days) in excess beyond 35 days between injections. ○ Length of time (in days) in excess beyond 35 days from last injection until start of oral bridging post Week 12. • For Q8W arm participants requiring oral lead-in: 
 ○ Length of time (in days) until next injection from date of dosage deviation (e.g. 2 mL administered instead of 3mL). ○ Length of time (in days) in excess beyond 63 days between injections post Week 16 and in excess beyond 56 days for Week 8 and Week 16 (e.g. missed or late injection visit). ○ Length of time (in days) in excess beyond 63 days from last injection until start of oral bridging post Week 16 and in excess beyond 56 days for Week 8 and Week 16. • For Q8W arm participants not requiring oral lead-in: 
 ○ Length of time (in days) until next injection from date of dosage deviation (e.g. 2 mL administered instead of 3 mL). ○ Length of time (in days) in excess beyond 63 days between injections. ○ Length of time (in days) in excess beyond 63 days from last injection until

Number	Exclusion Description
	
start of oral bridging post Week 16.
 
 • Interrupted days in oral study treatment (oral lead-in or oral bridging) if the oral dose has been interrupted for 3 or more consecutive days and the primary interruption reason is not adverse event or laboratory abnormality (based on the eCRF Exposure forms). 3 days will be assumed if such interrupted days are not available in the database.
03	Prohibited medications: receiving ART medication other than that prescribed/allowed by the study (excluding permanent changes in ART regimen; such cases will be retained as 'HIV1-RNA ≥ 50 c/mL' in the per protocol snapshot analysis) or receiving prohibited concomitant medication that would impact exposure or response to therapy with duration and route of administration taken into consideration, as recorded in the Protocol Deviation form in the eCRF based on study team review (where indicated in the PDMP as case-by-case determination).
04	Permanent discontinuation of IP/withdrawal due to a reason of "Protocol Deviation" (as recorded in the eCRF).
05	Other important protocol deviations that exclude Participant from Per protocol population as recorded in the Protocol Deviation form in the eCRF based on study team review (where indicated in the PDMP as case-by-case determination).

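### The Per-Protocol under-dosing count has no exception for injection gaps covered by oral bridging, so permitted bridged days score as under-dosing and some days can be counted twice

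*SAP*

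**What the plan says.** SAP 15.1.1, criterion 02 (3), divides non-compliant dosing days by intended exposure days and sets the threshold at 10% or more. The denominator is given as "Number of Intended Exposure Days = Date of Last Viral Load – Start Date of Study Treatment + 1", the viral load being the last on-treatment value up to Study Day 378 (Week 48 analysis) or Study Day 714 (Week 96 analysis).

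The numerator is a sum over all instances of several items, listed by arm and by oral lead-in status. Three matter here:

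- **Between injections.** Q8W with lead-in: "Length of time (in days) in excess beyond 63 days between injections post Week 16". Q4W with lead-in: "Length of time (in days) in excess beyond 35 days between injections post Week 12". Stricter limits of 56 and 28 days apply to the early post-lead-in injections. Participants without lead-in have the 63-day or 35-day limit throughout. None of these items mentions bridging.
- **Until bridging starts.** For Q8W: "Length of time (in days) in excess beyond 63 days from last injection until start of oral bridging post Week 16", with a matching 35-day item for Q4W.
- **Oral dosing gaps.** "Interrupted days in oral study treatment (oral lead-in or oral bridging) if the oral dose has been interrupted for 3 or more consecutive days", when the main reason is not an adverse event or laboratory abnormality.

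The text does not say that these items are mutually exclusive. The same section makes exclusion a case-by-case clinical determination after study-team review.

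**The concern.** The second and third items stop the clock when bridging begins and restart it only if the oral doses lapse. That is sensible only if a participant taking bridging tablets is compliant. The first item does not respect this: it measures from injection to injection whatever happened in between. A bridged interval therefore falls under the first item in full. Days past the limit but before a late bridging start fall under both the first and second items. Interrupted bridging days past the limit fall under both the first and third.

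Elsewhere the SAP keeps the distinction. Section 15.9 treats oral bridging as protocol-permitted and does not penalise it in the Snapshot. The injection-adherence categories in 15.6.4 separate missed injections with bridging from those without.

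At stake is who belongs to the Per-Protocol population. That analysis is the only one listed under sensitivity and supportive analyses for the primary endpoint (7.1.5.1), and 5.5.2 says its result will be compared with ITT-E for consistency. Two programmers could build different populations from the same text.

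**Working it through.** The SAP gives no worked figure for a bridged injection, so there is nothing to reproduce. The rule can be applied directly.

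**Inputs**
- Limits of 63 days (Q8W) and 35 days (Q4W), and the 10% threshold: 15.1.1.
- Injection spacing of 8 or 4 weeks, i.e. 56 or 28 days: 15.3.5. One wholly missed injection gives a gap of 2 × 56 = 112 days (Q8W) or 2 × 28 = 56 days (Q4W).
- Date of last viral load: the Week 48 Snapshot window is Study Days 295 to 378 and the Week 96 window 631 to 714 (15.3.2, Table 10). Target days are 7 × 48 + 1 = 337 and 7 × 96 + 1 = 673 (15.3.1). Because the denominator adds one day, it equals the Study Day of the last viral load.

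**Formula, as written:** percentage = (gap − limit) / Study Day of last viral load. The whole gap is assumed to fall before that viral load. For lead-in participants the main example concerns injections after Week 16 (Q8W) or Week 12 (Q4W).

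**One wholly missed and bridged injection**

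| | Excess days | Day 295 | Day 337 | Day 378 |
|---|---|---|---|---|
| Q8W | 112 − 63 = 49 | 16.6% | 14.5% | 13.0% |
| Q4W | 56 − 35 = 21 | 7.1% | 6.2% | 5.6% |

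Q8W meets the threshold across the Week 48 window; Q4W does not.

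**Same gap, bridged time treated as compliant.** If bridging starts within 63 days (Q8W) or 35 days (Q4W) of the last injection, with no countable oral interruption and no gap after bridging, the count is 0 in both arms.

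**Double counting.** Suppose bridging starts 70 days after the last Q8W injection, in a 112-day gap. The between-injections item gives 49 and the until-bridging item gives 70 − 63 = 7. The sum is 56 days, or 56/337 = 16.6%, with 7 days counted twice.

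**Where the arm contrast does not hold, even as written**
- Week 96: 49 days is 7.8%, 7.3% and 6.9% at Days 631, 673 and 714, all below 10%.
- Q8W after lead-in, Week 8 injection missed: the gap from Week 4B to Week 16 is 84 days, and 84 − 56 = 28 days, or 8.3% at Day 337.
- Short bridged delay in Q8W: a 70-day gap scores 7 days, or 2.1% at Day 337. At that day the gap must reach 63 + 34 = 97 days to meet 10%.
- Early last viral load in Q4W: 21/210 = 10.0%, so one missed Q4W injection also meets the threshold if the last viral load is on or before Day 210.
- Equal excess counts equally: two consecutive missed Q4W injections give 84 − 35 = 49 days, the same as one missed Q8W injection.

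**The case against.** The strongest reply is that the text, read as a whole, already sends bridged gaps to the bridging items. Criterion 02 concerns non-compliance, permitted bridging is not a deviation, the between-injections item is illustrated for lead-in participants by missed or late visits, and summing over instances naturally means summing over separate deviations. This is a fair account of the intent, and it is why the intended count is taken as 0 above. It does not supply the missing exception. If the first item covers bridged gaps, the second can only repeat days already counted. If it does not, the SAP should say so.

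Second, meeting 10% does not by itself remove anyone, because exclusion is decided case by case. That stands, and the consequence should be stated as meeting the threshold. It is only a partial answer: 15.1.1 also says the review is to confirm that cases meet the criteria, and a bridged Q8W participant does meet the criterion as written. The trial is open-label, so whoever resolves the ambiguity may know the arm.

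Third, the difference between arms belongs to one scenario and partly reflects that one Q8W injection covers twice the time. That also stands, as the exceptions above show.

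A reader might infer that the rule makes the two Per-Protocol arms non-comparable, or that it threatens the non-inferiority conclusion. The SAP supports neither. It gives no bridging frequency, so the number of participants affected is unknown, and non-inferiority is decided on ITT-E (5.5.1).

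**Conclusion.** The point holds as a drafting defect in a pre-specified numerical rule. As written, 15.1.1 criterion 02 (3) counts permitted bridged days past the 63-day or 35-day limit (or the stricter early limits) as under-dosing. It can also count days before a late bridging start, or interrupted bridging days past the limit, twice. The overlap exists in both arms and at both analysis timepoints.

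Its clearest consequence is at Week 48. One wholly missed and bridged Q8W injection scores 49 days against an intended 0 and meets the exclusion threshold, while one such Q4W injection scores 21 days and does not. This assumes that the whole gap precedes the last viral load, that the viral load falls in the Week 48 window, that the early post-lead-in limits do not apply, and, for the intended 0, that bridging starts in time and is uninterrupted. It should not be generalised to Week 96, to a missed Week 8 injection after lead-in, or to short delays. The effect on the size of the Per-Protocol population cannot be calculated from the SAP, and the ITT-E primary analysis is untouched. The correction is worth making before database freeze.

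**What to change.** In 15.1.1 criterion 02 (3):

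1. Limit every between-injections item, in both arms and with or without lead-in, to intervals that contain no oral bridging. Bridged intervals are then counted only by the until-bridging and interrupted-oral-dosing items.
2. State that no calendar day is counted under more than one item.
3. State how uncovered days between the end of bridging and the next injection are counted. At present only the between-injections item captures them, so the exception in step 1 would otherwise drop them. Any allowance for such days should come from the protocol's own dosing rules.

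The cost is a few words in the SAP and a small change to the Per-Protocol derivation. The existing rule already needs bridging start dates, and exposure to oral bridging is taken from the investigational product eCRF pages (15.6.4), so no new data should be required. No dosing rule changes.

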 - For participants transitioning from SOC on the Q8W arm, if the preceding injection occurs at Week 4B, the Delay in IP injection (days) will be calculated as:
 Delay in IP Injection (days) = Date of Week 8 injection - date of Week 4B injection - 28 days
 - For participants transitioning from SOC on the Q8W arm, if the preceding injection occurs at a visit later than Week 4B, the Delay in IP injection (days) will be calculated as:
 Delay in IP Injection (days) = Injection date - date of preceding injection - 56 days
 - For participants transitioning from CAB+RPV Q4W in ATLAS on the Q8W arm, the Delay in

IP injection (days) will be calculated as:
 Delay in IP Injection (days) = Injection date - date of preceding injection - 56 days

- Delay in IP injection will be grouped into: ≤1, 2-3, 4-7, >7 days.
- The proportion of participants with HIV-1 RNA ≥50 c/mL at Week 48 (Snapshot) will be summarized by last delay in IP Injection. The last delay in IP injection will be the delay in IP injection at Week 48, or the delay in last IP injection prior to Week 48 if a participant did not receive Week 48 injection (i.e. missing visit or withdrawal).

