15.6.5. Pharmacokinetic

This document is intended for planning analysis of PK concentration data only. Population pharmacokinetics and identification of important determinants of variability will be described in a separate document.

Pharmacokinetic Analyses		
Plasma CAB and RPV Concentration-time Data		
Plasma samples for determination of CAB and RPV concentration will be collected throughout the Maintenance Phase and at the withdrawal visit. Additional samples will be collected for storage during the Long-Term Follow-Up Phase.		
Evaluable Concentration		
PK concentration will be summarized in two ways: 'all data' without regard to timing relative to scheduled time and 'evaluable data'.		
The 'evaluable data' are from the samples that met sample collection window criteria. Sampling windows are set relative to the previous dose as follows:		

 • 20-28 hrs after last oral dose taken and properly administered last 3 oral doses for pre-dose sample at Week 4B for participants requiring oral lead-in • ± 4 days for pre-dose sample at visits other than Week 4B, and for pre-dose samples at Week 4B for participants not requiring oral lead-in (e.g. participants transitioning from ATLAS Q4W and remain on Q4W arm in this study) • 3-10 days post last injection for 1-week post injection visits; • Samples impacted by dosing errors (wrong dose) or oral bridging will also be excluded 		
Timepoint	Evaluable Window	For Programming:
Pre-dose: WK4B for participants requiring oral lead-in	20-28 hrs after last oral dose taken and the last 3 oral doses administered properly	$20 \text{ hrs} \leq \text{Time since Last Oral Dose} \leq 28 \text{ hrs}$ and the last 3 oral doses administered on the three consecutive days prior to WK4B.
Pre-dose at other visits, Pre-dose WK4B for participants not requiring oral lead-in	± 4 days	For Q4W arm, Day 1 pre-dose, and Week 8 for those transitioning from SOC (i.e. requiring oral lead-in) on Q8W arm: $24 \text{ days} \leq \text{Days Since Last Injection} \leq 32 \text{ days}$ For visits other than above on Q8W arm: $52 \text{ days} \leq \text{Days Since Last Injection} \leq 60 \text{ days}$
1-WK-Post:	3-10 days post last injection	$3 \text{ days} \leq \text{Days Since Last Injection} \leq 10 \text{ days}$
Relative Time is calculated relative to the date and time of last previous dose. For example, if the time of the last previous dose (e.g. oral lead-in/oral-bridging) is missing, then the relative time for		

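### The Per-Protocol under-dosing rule sets 56 days for the Week 8 injection in Q8W lead-in participants, while the passages that address the Week 4B to Week 8 interval treat it as 4 weeks

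*SAP*

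**What the plan says.** Criterion 02 in SAP 15.1.1 makes a participant a candidate for removal from the Per-Protocol population when under-dosed days reach 10% of intended exposure days. For Q8W participants with oral lead-in, days are counted when they are "in excess beyond 63 days between injections post Week 16 and in excess beyond 56 days for Week 8 and Week 16". The bullet on time from the last injection to oral bridging repeats the threshold: "until start of oral bridging post Week 16 and in excess beyond 56 days for Week 8 and Week 16".

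The same interval appears elsewhere for the same group:

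- 15.1.1, over-dosage part of criterion 02: an early injection is one with "length of time between Week 4B injection and Week 8 injection less than 3 weeks". After Week 8 the limit becomes 7 weeks.
- 15.3.5 and 15.6.3: planned injections fall at Week 4B, at Week 8, and every 8 weeks after that.
- 15.6.3, delay derivation: "Delay in IP Injection (days) = Date of Week 8 injection - date of Week 4B injection - 28 days".
- 15.6.5: "Week 8 for those transitioning from SOC (i.e. requiring oral lead-in) on Q8W arm" shares the evaluable pre-dose window of 24 to 32 days since the last injection. Most other Q8W visits have 52 to 60 days.

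For Q4W participants with oral lead-in, criterion 02 counts days "in excess beyond 28 days for Week 8 and Week 12" and allows 35 days after that.

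**The concern.** The Q8W line groups Week 8 with Week 16 under one threshold, although the planned interval before Week 8 is half the one before Week 16. An injection given 56 days after Week 4B is therefore 28 days late in the delay derivation and outside the PK window, yet has no non-compliant days in the Per-Protocol count. The same gap in a Q4W lead-in participant counts as 28 days.

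The Per-Protocol analysis is the only sensitivity analysis that 7.1.5.1 lists for the primary non-inferiority comparison, and it is to be checked for consistency with ITT-E. A rule that scores the same late visit differently by randomized arm weakens that check.

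**Working it through.** **Inputs.** Thresholds of 56 days (Q8W lead-in, Week 8) and 28 days (Q4W lead-in, Week 8), and the 10% cut-off: 15.1.1. Nominal Week 48 day, 7 × 48 + 1 = 337: 15.3.1. Latest day for the denominator, 378 (Week 48) and 714 (Week 96): 15.1.1. Nominal Week 96 day, 7 × 96 + 1 = 673. Earliest day of the Week 48 snapshot window, 295: Table 10.

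**Step 1: do the thresholds match the planned intervals?** Planned interval = 7 × (visit week − week of preceding injection).

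- Q4W, Week 4B to 8: 7 × 4 = 28. Stated 28, reproduced.
- Q4W, Week 8 to 12: 7 × 4 = 28. Stated 28, reproduced.
- Q8W, Week 8 to 16: 7 × 8 = 56. Stated 56, reproduced.
- Q8W, Week 4B to 8: 7 × 4 = 28. Stated 56, not reproduced.

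The early thresholds otherwise equal the planned interval with no grace, and 7 days are added only later (35 and 63). The Q8W Week 8 entry alone breaks the pattern.

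**Step 2: days not counted.** Non-compliant days = max(0, gap − threshold).

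| Week 4B to Week 8 gap (days) | Counted from 28 | Counted from 56 | Difference |
|---|---|---|---|
| 35 | 7 | 0 | 7 |
| 42 | 14 | 0 | 14 |
| 49 | 21 | 0 | 21 |
| 56 | 28 | 0 | 28 |
| 62 | 34 | 6 | 28 |
| 90 | 62 | 34 | 28 |

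**Step 3: effect on the 10% criterion.** Days needed = 10% of exposure days, rounded up. The gap that meets the criterion alone = threshold + days needed.

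| Exposure days | Days needed | Gap, from 28 | Gap, from 56 | 28 days as % of exposure |
|---|---|---|---|---|
| 280 | 28 | 56 | 84 | 10.0 |
| 295 | 30 | 58 | 86 | 9.5 |
| 337 | 34 | 62 | 90 | 8.3 |
| 378 | 38 | 66 | 94 | 7.4 |
| 673 | 68 | 96 | 124 | 4.2 |
| 714 | 72 | 100 | 128 | 3.9 |

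At 337 days, a single gap of 62 to 89 days gives 34 to 61 counted days from 28 (10.1% to 18.1%), but 6 to 33 from 56 (1.8% to 9.8%). The 28 days reach 10% alone only when exposure is 280 days or less, which is before the Week 48 window opens at Day 295.

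**The case against.** The best counter-argument is a second reading: the words may mean intervals that start at the named visits. Weeks 8 to 16 and 16 to 24 are both 56 days, and in Q4W Weeks 8 to 12 and 12 to 16 are both 28, so no number is then contradicted. This cannot be ruled out. It fits less well with the bullets' own example of a missed or late injection visit. It would also leave Week 4B to Week 8 with no under-dosing threshold in either arm. The imbalance between arms would go, but the gap in the text would remain.

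Several limits on the effect stand. One interval in one subgroup is involved. The count stops when oral bridging starts. Exclusion is decided case by case, and criterion 05 allows other deviations to be considered. These may reduce the consequences, but they do not correct the count that the study team is asked to confirm.

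A reader might go further than the text allows:

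- That a late Week 8 injection never counts in Q8W. This is so only for gaps up to 56 days; beyond that, 28 fewer days are counted.
- That the whole SAP uses 28 days here. The Q8W last-injection rules, such as Table 16, use 63 days with no Week 4B exception, but they set treatment state or follow-up, not this dosing interval.
- That modest lateness readily changes membership. An injection 28 days late plus 6 later non-compliant days gives 34/337 = 10.1% against 6/337 = 1.8%, but the 34 days fall below 10% from 341 exposure days on (34/341 = 9.97%).
- That the non-inferiority conclusion is biased. It rests on ITT-E, and the documents do not show how many participants had such gaps.

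**Conclusion.** The contradiction is real: both Q8W lead-in bullets in criterion 02 conflict with the sections that address the Week 4B to Week 8 interval. Read as intervals ending at the named visits, up to 28 late days are left out of the Q8W count and included in the Q4W count. Read the other way, the interval has no threshold in either arm.

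The size is moderate to small: 7.4% of exposure at Day 378 and about 4% at Week 96. It bears mainly on participants with other non-compliant days, a long gap or short exposure. The single-gap range of 62 to 89 days assumes 337 exposure days, no oral bridging within the gap and no other non-compliant days. The effect is confined to the Per-Protocol analyses and can be tempered by review. Neither the number of participants affected nor the direction of any change in the estimate can be derived from the SAP.

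**What to change.** In both Q8W lead-in bullets of criterion 02 (late or missed injection, and time to oral bridging), give the Week 4B to Week 8 interval its own entry, separate from Week 16. Say explicitly whether a named visit ends or begins the interval, and word the Q4W bullets the same way. Reconcile the reference length with the over-dosage part of criterion 02 and with 15.3.5, 15.6.3 and 15.6.5, so that the Per-Protocol count, the delay derivation and PK evaluability use one interval. Which length is clinically right is for the sponsor to settle.

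The cost is a wording change and about one line of derivation code. It should be made before the final deviation review that precedes database freeze. Whether anyone's Per-Protocol status changes depends on the reconciled interval and the data.
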